4 SELECTION AND ENROLLMENT OF PARTICIPANTS

The IPPI intervention targets distress of PLWD. As a result, champion(s) will be trained to identify residents in each of the participating nine communities that have both cognitive impairment (Brief Inventory for Mental Status (BIMS) score of 0-12) and who have recently triggered for distress as reported in Section D (non-zero response on PHQ-9 items of anhedonia, sad mood, poor self-esteem, poor appetite, or restlessness) or Section E (non-zero response on a behavior) in the MDS 3.0.

Inclusion Criteria

Participants of any age, race, gender, or ethnicity will be eligible for enrollment if the following criteria are met:

- The individual is a long-stay resident in one of the nine participating UCH NH locations partnering with the PI for this project.
- The most recent MDS 3.0 assessment indicates a BIMS score of 0-12 *and* a non-zero response on PHQ-9 items of anhedonia, sad mood, poor self-esteem, poor appetite, or restlessness or Section E behavior item(s).

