6.2.3 Follow-up Visits

- IPPI completions 2x weekly:
 - The Fidelity Assessment with Pragmatic Checklist will be completed the first time a member of the intervention team completes an IPPI with a resident. This will be completed by the site champion when shadowing the care partner in implementation.
 - IPPIs will be documented in the UCH EMR through Point-Click-Care.
 - During implementation, troubleshooting (count of contacts of the implementation teams with the PI/Project team) will be recorded.
 - If an eligible resident is withdrawn from participation, the withdrawal date, and the reason will be documented on an Intervention Withdrawal form and provided to the project PI. This form is part of the binder that will be provided to each site champion(s).
 - Adverse Events will be reported directly to the PI if they occur as per section 7.3 below.
- 3-months (~90 days):
 - Distress data (Section E and Section D) from the next completed MDS 3.0 assessment (annual or quarterly) will be provided to the PI by the UCH IT Corporate office. The Centers for Medicare and Medicaid Services require completion of an assessment every 3-months; however, experience indicates that there is individual variability in actual completion times and therefore we will not enforce a strict allowable time window for these data. Change in each Section E/Section D item will be scored as 0 = *stayed the same as baseline* (e.g., score on MDS 3.0 baseline assessment equals score on MDS 3.0 follow-up assessment), 1 = *got better* (e.g., score on MDS 3.0 baseline assessment is better (lower) than the score on the MDS 3.0 follow-up assessment), or 2 = *got worse* (e.g., score on MDS 3.0 baseline assessment is worse (higher) than the score on MDS 3.0 follow-up assessment) for our primary, person-centered clinical outcome.
- 6-months (~180 days):
 - Distress data (Section E and Section D) from the next completed MDS 3.0 assessment (annual or quarterly ~6-months post baseline assessment) will be provided to the PI by the UCH IT Corporate office. The Centers for Medicare and Medicaid Services require completion of an assessment every 3-months; however, experience indicates that there is individual variability in actual completion times and therefore will not enforce a

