strict allowable time window for these data. Change in Section E/Section D items will be scored as 0 = *stayed the same as baseline* (e.g., score on MDS 3.0 baseline assessment equals score on MDS 3.0 follow-up assessment), 1 = *got better* (e.g., score on MDS 3.0 baseline assessment is better (lower) than the score on the MDS 3.0 follow-up assessment), or 2 = *got worse* (e.g., score on MDS 3.0 baseline assessment is worse (higher) than the score on MDS 3.0 follow-up assessment) for our primary, person-centered clinical outcome.

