9 STATISTICAL CONSIDERATIONS

9.1 General Design Issues

The primary objective is to effectively deploy the IPPI program so that care providers can use the program as a part of their routine care delivery. We hypothesize that implementation will result in decreased expressions of behavioral distress and/or depressive symptoms for residents engaged in the program at 3-month and 6-month intervention follow-up and increased knowledge of emotion-focused communication and self-efficacy for using emotion-focused communication for care providers.

Our secondary objective is to demonstrate program feasibility and fidelity as well as document barriers and facilitators in implementation.

For this pilot study, we will have a non-randomized, within-person design, examining how individual levels of distress change from baseline to 3-months to 6-months. We will report rates of overall sample change versus stability. No randomization will occur for this trial, as the primary purpose is to establish pragmatic feasibility of the intervention.

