The primary clinical outcome will be reports of distress as rated in the residents' MDS 3.0 annual or quarterly assessments in Section E and Section D (Saliba & Buchanan, 2009). These items will also be rated by the implementation team care partner delivering the intervention. These data will be collected at baseline (to determine eligibility) and at 3-months and 6-months post-intervention enrollment. The items in Section D and Section E are validated standardized items used to assess all NH residents in the United States receiving funding from the Centers for Medicare and Medicaid Services. Section D depression item responses are drawn from the widely used and validated PHQ-9 (Kroenke et al., 2001; anhedonia, sad mood, poor self-esteem, poor appetite, or restlessness). The items ask *“Over the past 2 weeks, have you been bothered by any of the following problems?”* and then if the resident responds “yes” they are asked *“About how often have you been bothered by this?”*. Item level scores are 0 (*did not occur*), 1 (2-6 days), 2 (7-11 days), or 3 (12-14 days). The Section E behavior items have been used as a valid indicator of behavioral distress (Saliba & Buchanan, 2009). Items include the presence of verbal, physical or other behavior symptoms directed toward others, rejection of care, and wandering. For section E, each behavior is rated with a 0 (*did not occur in the past week*), 1 (*occurred 1-3 days in the past week*), 2 (*occurred 4-6 days*) or 3 (*occurred daily*). For each resident care partners will have designated a targeted mood or behavior item selected for improvement and assessed via MDS data. The targeted mood or behavior selected by the care partner at baseline will be reassessed at 3-months and 6-months and recorded as 0 = *stayed the same as baseline* (e.g., score on MDS 3.0 baseline assessment equals score on MDS 3.0 follow-up assessment), 1 = *got better* (e.g., score on

MDS 3.0 baseline assessment is better (lower) than the score on the MDS 3.0 follow-up assessment), or 2 = *got worse* (e.g., score on MDS 3.0 baseline assessment is worse (higher) than the score on MDS 3.0 follow-up assessment) for our primary, person-centered clinical outcome. The type of mood or behavior item being tracked will be different for each resident (e.g., wandering for one, verbal behavior for another)

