9.4.1 Primary outcome

The primary clinical outcome will be reports of distress as rated in the residents' MDS 3.0 annual or quarterly assessments in Section E and Section D (Saliba & Buchanan, 2009). These items will also be rated by the implementation team care partner delivering the intervention. These data will be collected at baseline (to determine eligibility) and at 3-months and 6-months post-intervention enrollment. For each resident, a targeted mood or behavior item selected for improvement and assessed via MDS data will be used as the primary outcome. The targeted mood or behavior will be recorded as 0 = *stayed the same as baseline* (e.g., score on MDS 3.0 baseline assessment equals score on MDS 3.0 follow-up assessment), 1 = *got better* (e.g., score on MDS 3.0 baseline assessment is better (lower) than the score on the MDS 3.0 follow-up assessment), or 2 = *got worse* (e.g., score on MDS 3.0 baseline assessment is worse (higher) than the score on MDS 3.0 follow-up assessment) for our primary, person-centered clinical outcome at 3-months and 6-months post

intervention enrollment. The type of mood or behavior item being tracked will be different for each resident (e.g., wandering for one, verbal behavior for another).

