9.5 Data Analyses

Analysis of data will be descriptive. To address our first objective of clinical impact for residents, we will code a change score for each enrolled resident's targeted behaviors (e.g., improved, stayed same, worsened) in two ways. We will use the MDS 3.0 data between baseline and 6 months. We will report aggregate percentages of improved, stayed same, and worsened from the MDS 3.0 data. For implementation team members, the outcomes of knowledge and self-efficacy will be analyzed through paired samples t-tests of pre- and post-EFCT test measures.

For our second objective of feasibility and fidelity, we will calculate the number of residents each NH is able to engage as a percentage of the goal (e.g., 15 residents minimum) via data collected from the Resident Preferences Worksheet. We will also calculate the percentage of the implementation team that completed the EFCT based on data from the EFCT LMS. Finally, we will calculate the average number of IPPIs completed (via the EMR). Acceptability, feasibility, and appropriateness will be calculated according to responses from the exit interview (Weiner et al., 2017; AIM, IAM, and FIM measures). Qualitative data collected by the semi-structured exit interview

will be audio recorded, transcribed verbatim, and coded for facilitators and barriers in Dedoose.

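### Sections 9.4.1 and 9.5 commit to a report only for the items staff select to improve, so the percentages lean toward improvement and change on a resident's other items has no committed report

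*Combined protocol and SAP*

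**What the plan says.** The item scope of the resident outcome differs between sections.

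- **6.2.3, 3 months:** "Change in each Section E/Section D item will be scored as" the same, better or worse. **6 months:** "Change in Section E/Section D items will be scored as" in the same way. Both entries end "for our primary, person-centered clinical outcome". Neither is limited to a target.
- **9.1:** "For each resident care partners will have designated a targeted mood or behavior item selected for improvement and assessed via MDS data". The same section also promises: "We will report rates of overall sample change versus stability". It names no items for that.
- **9.4.1:** "For each resident, a targeted mood or behavior item selected for improvement and assessed via MDS data will be used as the primary outcome".
- **9.5:** "we will code a change score for each enrolled resident's targeted behaviors (e.g., improved, stayed same, worsened) in two ways". It then promises aggregate percentages improved, unchanged and worsened from the MDS.
- **9.4.2:** no resident mood or behavior outcome is listed.
- **10.2:** Section D and E data are extracted for enrolled residents at both follow-ups.

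On choosing the target, section 3 has the champion's form record the item that distresses the resident most. The Appendix A worksheet asks for one or more behaviors shown on MDS Section E. It offers five behavior boxes and one box for depressive mood symptoms as a group. Inclusion requires a non-zero score on at least one of five mood items or on a Section E behavior. No rule requires the target itself to be above 0.

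**The concern.** Items run from 0 to 3. An item at 0 can only stay the same or get worse; an item above 0 can also improve. If the reported items are mostly ones chosen because they were a problem at baseline, the planned percentages draw mainly on the part of the scale where improvement is possible and new onset is not.

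The resident hypothesis concerns behavioral distress and/or depressive symptoms, not one chosen item. A resident whose targeted sad mood falls from 2 to 1 while untargeted wandering rises from 0 to 1 would appear in the 9.5 report only as improved. Section 9.2 says the findings will inform power for a full-scale trial, so an improvement rate shaped by item choice could be carried forward. An analyst starting from 6.2.3 and one starting from 9.5 could also build different primary tables.

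**Working it through.** **Plan's own figure.** There is none to reproduce. The resident analysis is descriptive, with no expected improvement rate, item distribution or effect size.

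**From the documents.** Five Section D and five Section E items, each scored 0 to 3 (9.1); at least one non-zero item at entry (section 4); no control group (9.1).

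**Items outside the committed report, per resident.** One target: 10 − 1 = 9. Mood box plus *b* behavior boxes: 5 − *b* Section E items, which is 0 if all six boxes are ticked. Targets differ between residents, so any item can still enter the sample aggregate.

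**No-change model (all inputs assumed).** Each item is cut from a bivariate normal with the same margins at baseline and follow-up. P0 = share at 0 = 0.6, 0.7, 0.8 or 0.9. Latent correlation = 0.4, 0.6 or 0.8. Non-zero scores split 50/30/20 or in equal thirds.

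With no true change, better and worse are equally common among all residents on an item; call each *m*. Let *o* = P(follow-up above 0, given baseline 0). Screening for at least one of K independent items above 0 drops only residents at 0 on all K, and they could contribute only onsets. So, averaged per item:

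- better = m / (1 − P0^K)
- worse = (m − P0^K × o) / (1 − P0^K)
- gap = P0^K × o / (1 − P0^K)

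K = 1 is a single target above 0, K = 5 the mood box, K = 10 all items.

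**Example:** P0 = 0.8, correlation 0.6, 50/30/20 split. Here m = 13.0% and o = 12.6%.

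- K = 1: better 13.0/0.2 ≈ 65.1%, worse 14.7%, gap 0.8 × 12.6/0.2 = 50.4 points
- K = 5: 0.8^5 = 0.328; gap 0.328 × 12.6/0.672 = 6.1 points
- K = 10: 0.8^10 = 0.107; gap 0.107 × 12.6/0.893 = 1.5 points
- Share of all worsening on the item that starts from 0: 0.8 × 12.6/13.0 = 78%

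If a share *q* of single targets starts at 0, better = (1 − q) × better and worse = (1 − q) × worse + q × o. For q = 0.25: 48.8% against 11.0 + 3.2 = 14.2%, a gap of 34.6 points.

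**Ranges over the grid**

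| Reported set | Better, % | Worse, % | Gap, points |
|---|---|---|---|
| Single target, all above 0 | 43–82 | 8–19 | 25–73 |
| 10% of targets at 0 | 39–74 | 8–19 | 21–65 |
| 25% of targets at 0 | 32–61 | 8–20 | 14–53 |
| Mood box, item by item | 14–27 | 7–24 | 1–12 |
| All ten items (50/30/20 split) | 9–25 | 7–25 | 0.1–4.4 |

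Between 57% and 90% of all worsening on an item starts from 0.

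**Higher correlation.** At 0.9 with P0 = 0.6, o = 11.6%, so the single-target gap is 0.6 × 11.6/0.4 = 17 points (34% against 16% with the 50/30/20 split).

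**Second check.** A simulation with correlated items (between-item correlation 0.2, item prevalence 15% or 30%, test-retest 0.4 to 0.8) and the target set to the worst or a random non-zero item gave 50–84% improved against 5–17% worsened. All ten items together gave 12–22% against 10–21%. The direction was the same in every scenario. In those residents, 48–81% had new onset on at least one non-targeted item.

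**The case against.** **The conflict may be loose drafting.** Section 6.2.2, just before 6.2.3, says the baseline data include the targeted item, and 9.1 and 9.4.1 attach the same primary-outcome label to the target. Targeted-only is the more natural reading. That stands, but 6.2.3 still needs one clarifying line.

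**Silence is not exclusion.** A reader might infer that the plan rules out reporting other items. It does not: 9.5 is silent, 6.2.3 scores the items and 10.2 extracts them. Nor does the broader text commit to a report. The overall-change sentence in 9.1 names no items, and the two ways of coding in 9.5 both concern targeted behaviors.

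**Nine of ten items do not vanish.** A reader might infer that from the count. It is per resident with one target.

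**The size is assumed.** This stands in full. The gap shrinks as correlation rises and is small for the mood box, which can include items at 0. How often that box is ticked is unknown.

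**Harm is not unmonitored.** Monthly calls ask about unexpected changes (7.3), significant deterioration is recorded as an adverse event (7.3.2), and worsening on the target is reported. The question after each session (9.1) and the first-session checklist (Appendix A) add some capture. These cover single sessions or events staff notice; they do not replace item scores.

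**Little turns on the percentage.** The study is a descriptive feasibility pilot with no test or decision rule on this outcome. Section 9.2 does not say that the targeted improvement rate will be the planning effect size. This limits the weight of the point.

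**Conclusion.** The point holds in limited form. Sections 9.4.1 and 9.5 commit to a report for selected items only, while 6.2.3 attaches the primary label to Section D and E items generally. Because targets will usually be above 0, the targeted percentages favour improvement with no true change, partly through regression to the mean. New onset or worsening on a resident's non-targeted items has no committed report.

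The direction follows from the scale and the selection; the size does not come from the documents. Under the assumed no-change model it is about 17 to 73 points for a single target above 0 (correlation 0.4 to 0.9) and 1 to 12 points for the mood box (0.4 to 0.8). It falls further if some single targets start at 0.

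A reader might infer that the targeted item is a wrong choice of primary outcome, or that a false-positive rate is inflated. Neither follows: a person-centered target is reasonable, and no resident test is planned. This is a modest improvement.

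**What to change.** 1. **6.2.3:** state that the targeted item is primary and that item scoring feeds a supporting table.
2. **9.5:** add one descriptive table, at 3 and 6 months, for all enrolled residents with a follow-up MDS. For each of the five Section D and five Section E items, regardless of targeting, give n (%) better, same and worse, and n (%) with new onset among residents at 0 on that item at baseline, showing that denominator.
3. **6.2.3, 9.1 and 9.4.1:** correct the bracketed examples, which currently call a baseline lower than follow-up better. Better should mean follow-up lower than baseline; otherwise the new table inherits the reversal.
4. **Caveat for both directions:** without a control group, neither improvement on the targeted item (expected in part from regression to the mean) nor worsening on other items can be attributed to the program. The targeted improvement rate should not be used alone to plan the full-scale trial.

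The table does not remove the tilt from the primary percentage, so the caveat is needed. Including the table in the data safety submission (9.3) is optional.

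Cost: a few lines and one table from data already extracted, with no new visits or staff time at sites. The downside is that natural fluctuation and disease progression will show as some worsening that cannot be attributed to the program.

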provided IPPI activity training videos (each 10-15 min), and be provided the IPPI manual with a checklist of steps, 60+ different IPPI protocols that address all 16 MDS 3.0 preferences in Section F, sample letters/scripts introducing the IPPI to family and staff, and communication tips sheets. Any member of the implementation team can deliver an IPPI activity. We will ask champion(s) to demonstrate an IPPI for care partners (e.g., CNAs) to watch, and then observe each care partner's initial IPPI implementation.

The champion(s) will be provided with a pragmatic data collection binder of paper forms (See Appendix A) to record these initial observations (in the form of a checklist). In addition, this binder will include a form to document staff training completion, resident preferences, and the behavior or mood item to target with the IPPI program that is most distressing to each identified eligible resident. Forms for champion(s) to document adverse events and withdraws will also be included in the binder.

Implementation team members will align stated preferences of each eligible resident with specific IPPI protocols (i.e., important preference for reading will be matched with a reading activity IPPI protocol). While any implementation team member can deliver an IPPI activity, we will encourage care partners to take the lead in implementation of the preferred IPPI activity with each enrolled resident on a regular basis. Initiation of engagement will be rolling, adding 3-7 residents per month for 3-4 consecutive months. The care partners will implement a minimum of 2 IPPI protocols per week with each resident for 6 months, to ensure continuous completion of the intervention through to the date of the resident's next two quarterly or annual MDS 3.0 assessment (3-month and 6-month follow-up data). The project manager will provide virtual coaching to communities throughout implementation as needed. Table 1 below outlines the intervention structure and implementation strategy. In addition, we identify the implementation measure/metric we will track during the course of implementation.

Table 1. IPPI Intervention Structure, Implementation Strategy, and Implementation Measures

Intervention Structure	Implementation Strategy	Implementation Measure
Establish Co-champions	Assess Organizational Readiness	Organizational Readiness for Implementing Change (ORIC) ³⁰

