6.2.2 Enrollment, Baseline, and/or Randomization

Enrollment

There will be a waiver of consent for all residents enrolled in the program. Upon identification of eligibility, the implementation team uses the Resident Preferences Worksheet to identify next steps. This will be a rolling process as individuals are identified as eligible to participate. Each enrolled individual will have a Worksheet completed at their specific time of enrollment. In this Worksheet, members of the implementation team will identify the resident's important preferences and identify matching IPPI protocols that can be used. They will also identify the behavior they hope to target with the IPPI intervention. A copy of the care plan will be obtained to ensure that the targeted behavior is addressed. The PI will collect this Worksheet from champions to determine whether or not the IPPI protocols were appropriately matched to important resident preferences as a measure of implementation fidelity every three months.

Baseline Assessments

The baseline assessment for residents will be their most recent MDS 3.0 (either

annual or quarterly). The BIMS and Section D/Section E responses will be provided to the PI for each enrolled resident by the UCH IT professionals. These data will include the targeted mood or behavior selected by care partners at enrollment. The type of mood or behavior item being targeted will be different for each resident (e.g., wandering for one, verbal behavior for another).

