***email address will be used to identify if individual completed the Emotion Focused Communication Training**

IPPI Program – Resident Preferences Worksheet

Site champion(s) will maintain a password protected list of the name of each resident that is enrolled into the IPPI program along with a unique ID# that is determined by the champion(s). This password protected file will be shared with the PI who will then link the data from this worksheet to the electronic medical record data prior to deidentifying.

After completing a resident's preference assessment, identify and record their most important preferences in the column "Important Preferences." Next, review the list of IPPI protocols then record the protocols that match the resident's important preferences in the "Matching IPPIs" column. Review the list of matching IPPIs with the implementation team member(s) that will be facilitating the activity with the resident and let them chose which IPPI activities (1-2) they are most comfortable doing. After they've chosen the IPPI activities, record their selection in the "IPPIs Selected" column. Identify one or more resident behaviors that are the target outcome for the intervention as indicated on the MDS Section E. Finally, note if the resident completed the project and if there were any adverse events.

Resident Unique ID#	Important Preferences	Matching IPPIs	IPPIs Selected by implementation team	Supplies Needed Location	Which targeted behavior(s) do you hope the IPPI will remediate? Check all that apply	Did the resident complete the IPPI Project? Yes No If no, why did the individual not complete the project?	Did the resident have any adverse events? Yes No If Yes, complete Serious Adverse Event Report Form
	•	•	•	○	 Physical behavioral symptom  Verbal behavioral symptom  Other behavioral symptom  Rejection of Care  Wandering  Depressive Mood Symptoms	○	○

Observation Checklist of Fidelity to IPPI Protocol conducted by Champion

Did the person delivering the IPPI do any of the following?

1. Yes No N/A Introduce self to resident
2. Yes No N/A Introduce IPPI activity to resident
3. Yes No N/A Consider possible distractions (background noise, visual/tactile)
4. Yes No N/A Check that individual could hear or was wearing hearing aids if applicable
5. Yes No N/A Interrupt resident in the middle of a visit (reverse coded)

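### The score rule for the primary resident outcome is written backwards (*got better* = baseline lower than follow-up); a lesser point is that section 9.5 should say its uncontrolled percentages are not evidence of an IPPI effect

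*Combined protocol and SAP*

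**What the plan says.** **Outcome.** Section 9.4.1: "For each resident, a targeted mood or behavior item selected for improvement and assessed via MDS data will be used as the primary outcome". Section 9.1 gives the scales. Section D mood items run 0–3 by number of days in the past two weeks; Section E behaviour items run 0–3 by number of days in the past week. In both, 0 means the symptom did not occur and a higher score means it occurred more often.

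**Coding.** Code 0 is no change. Code 1, *got better*, is glossed as "score on MDS 3.0 baseline assessment is better (lower) than the score on the MDS 3.0 follow-up assessment". Code 2, *got worse*, is glossed as the mirror image, with the baseline score higher than the follow-up score. The same pair stands in 6.2.3 (once for 3 months, once for 6 months), in 9.1 and in 9.4.1.

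**Selection and baseline.** The inclusion criteria in section 4 require at least one non-zero mood or behaviour item on the latest MDS. Section 6.2.2: "The baseline assessment for residents will be their most recent MDS 3.0". Section 9.4.1: "These data will be collected at baseline (to determine eligibility) and at 3-months and 6-months post-intervention enrollment". Staff choose the target at that point. Section 3 says the binder records "the behavior or mood item to target with the IPPI program that is most distressing to each identified eligible resident", and the Resident Preferences Worksheet in Appendix A says "Identify one or more resident behaviors that are the target outcome for the intervention as indicated on the MDS Section E".

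**Analysis.** Section 9.5 introduces the resident analysis as addressing clinical impact and then says: "We will report aggregate percentages of improved, stayed same, and worsened from the MDS 3.0 data". It covers enrolled residents only. Sections 9.4 and 9.5 call the analysis descriptive, and 9.1 calls the design non-randomized and within-person and gives feasibility as the primary purpose. Sections 1.1 and 9.1 nevertheless hypothesise that implementing IPPI will reduce distress.

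**The concern.** There are two points of unequal weight.

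1. The only score rule in the document for *got better* and *got worse* contradicts the labels. Section 9.5 does not restate it, so anyone coding the data from the protocol would take it from 6.2.3, 9.1 or 9.4.1. Applied as written, it exchanges the two informative categories of the primary clinical outcome.

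2. Even correctly coded, the percentages come from one group, chosen because something was non-zero on the assessment that is also the baseline. Scores in such a group move without any intervention effect. No sentence mentions regression to the mean, natural course or the missing comparator, and none says the percentages leave the resident hypothesis untested. At stake is how the clinical result is reported, and whether it is later taken as an effect size: section 9.2 says findings will inform the power of the full-scale trial.

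**Working it through.** **Step 1. The rule applied to scores** (scale from 9.1, rule from 9.4.1).

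| Baseline | Follow-up | What happened | Code under the rule as written |
|---|---|---|---|
| 3 | 1 | symptom less frequent | baseline higher than follow-up: *got worse* (2) |
| 1 | 3 | symptom more frequent | baseline lower than follow-up: *got better* (1) |
| 2 | 2 | no change | *stayed the same* (0) |

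Every resident with a change is misclassified; *stayed the same* is unaffected. This needs no assumption beyond the document's own scale.

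**Step 2. Selection with no intervention effect.** The documents give no expected percentage, alpha, power or effect size for the resident outcome, so there is no planned figure to reproduce. All inputs here are assumptions:
- One 0–3 item is measured twice, with the same distribution each time.
- The item is non-zero in a fraction q of residents, with non-zero scores split 60/25/15% over levels 1, 2 and 3.
- The latent follow-up value is f = r·b + √(1 − r²)·e, where b is the latent baseline value and e is independent noise.

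Mid-case, q = 0.20 and r = 0.7:
- All residents: improved 0.117, worsened 0.117. The two are equal, as no effect and no drift require.
- Residents with a non-zero baseline: improved 0.587, same 0.266, worsened 0.147.

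The mechanism can be checked by hand. A score of 0 cannot fall, so all the improvement lies among the non-zero residents: 0.117 / 0.20 = 0.585, which is the simulated 0.587 up to rounding and simulation error. Of the worsening, only 0.147 × 0.20 = 0.029 lies in that group. The other 0.117 − 0.029 = 0.088 starts from a score of 0 and drops out.

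Under the rule as written, this mid-case would be reported as 15% better and 59% worse.

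**Step 3. Range without drift.** Over q from 0.1 to 0.5 and r from 0.3 to 0.9, improved runs from 28% (q = 0.5, r = 0.9) to 85% (q = 0.1, r = 0.3), and worsened from 6% to 18%.

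**Step 4. Natural worsening.** A second no-effect simulation used ten items, with 85% or 70% zeros, correlation 0.4, 0.6, 0.8, 0.9 or 0.95, and the target taken as a random non-zero item or the highest item. That makes 2 × 5 × 2 = 20 scenarios.

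| Drift (latent SD) | Improved | Worsened | Improved larger in |
|---|---|---|---|
| 0 | 29–79% | 8–18% | 20 of 20 |
| 0.25 | 10–71% | 12–36% | 12 of 20 |
| 0.5 | 2–62% | 17–60% | 7 of 20 |

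If the target may be any item, including one scored 0, then without drift improved is 7–23% and worsened 7–20%, a gap of 0.5–5 points.

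**Step 5. Sampling error for scale.** At n = 108 and p = 0.5, the 95% half-width is 1.96 × √(0.25/108) = 0.094. The spread of percentages compatible with no effect is much wider than that.

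**The case against.** **On the coding.** The score comparison is introduced as an example, the labels themselves are clear, and 9.5 speaks simply of improved and worsened. An analyst may well code by plain meaning. That is fair, and the documents do not show that any data were coded the wrong way. But the comparison is the only operational definition given, it is wrong each time it appears, and it defines the primary clinical outcome.

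**On the percentages.** The plan is openly a descriptive, non-randomized feasibility pilot. It sets no test, interval or success threshold for residents, and it leaves effectiveness to a later trial. Most of this stands: what is missing is a statement of interpretation, and no planned analysis is invalid.

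A reader might infer more than the text supports:
- *That the pilot is a concealed efficacy test.* Sections 9.1, 9.4 and 9.5 do not read that way.
- *That the result must be biased towards benefit.* Selection favours improvement only if the target is non-zero. Eligibility requires some non-zero item; for the target itself this is implied by the choice of the most distressing item, but no rule says so. Natural worsening can offset or reverse the tilt, and section 8 expects withdrawals through death, health change and transfer, which the simulations leave out.
- *That these percentages will power the next trial.* Section 9.2 speaks of findings in general and does not name them.

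**Conclusion.** The coding rule is wrong as written in all four places. Applied literally, it exchanges the improved and worsened percentages in full; that follows from the document's own scale.

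The second point holds at lower severity. With selection and baseline on the same MDS and no comparator, the percentages in 9.5 describe the enrolled group but cannot support or refute the resident hypothesis in 1.1 and 9.1. The net direction and size of the non-intervention change are unknown. The simulated figures rest wholly on assumed prevalence, correlation and drift. They show only that a wide range of results is compatible with no effect, and they do not estimate a bias in this trial. The feasibility, fidelity and staff outcomes are not touched.

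**What to change.** 1. In 6.2.3 (3 and 6 months), 9.1 and 9.4.1, define *got better* as a follow-up score lower than baseline and *got worse* as a follow-up score higher than baseline. If coding has begun, check its direction against the raw item scores. Cost: four wording corrections.

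2. In 9.5, add that the percentages are uncontrolled, are subject to regression to the mean and natural drift, and will not be read as evidence of an IPPI effect or used as the effect size for the full-scale trial. Word the Précis (Objectives; Design and Outcomes), 1.1 and 9.1 to match. Cost: one sentence and a few aligned edits.

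3. Report the targeted item's 3- and 6-month score by its baseline score, so that targets at 0 (which cannot improve) and at 3 (which cannot worsen) are visible. Show Sections D and E separately, because their look-back periods differ. Cost: one table from data already planned. The downside is small cells: with 108 residents, two sections and four baseline scores, a row averages 108 / 8 = 13.5 residents, and some will hold far fewer.

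Under section 11.1, protocol modifications go to the IRB. No new data, design change or added residents are needed.
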